8.0 STATISTICAL ANALYSIS PLAN

Overview

This is a single-arm Phase II study of pembrolizumab in combination with standard adjuvant hormonal therapy in patients with inflammatory breast cancer (IBC). The primary endpoint is Disease-free survival (DFS) as evidenced by the patient remaining alive with continued disease control. We will use a Bayesian time-to-event monitoring design to monitor DFS to ensure patient safety. Continued disease control will be defined as no disease by imaging.

Sample Size and Power

With a total of 37 patients, assuming 80% are alive and disease-free at two years, and all patients are followed for more than 2 years after study enrollment with no dropout, a 95% confidence interval around the 2-year estimate of disease-free survival will be approximately 25% wide.

Disease-Free Survival Monitoring Rule

The primary outcome is T = the time to disease relapse. The Bayesian method of Thall, et al.¹ will be used for safety and efficacy monitoring. For the purpose of safety and efficacy monitoring, “failure” will be defined as $F2YR = [T < 2 \text{ years}]$. The historical DFS rate in this population treated in MD Anderson Cancer center (1989-2011) for standard therapy is 60% at two years, corresponding to a failure (disease relapse) rate of 40% at two years¹³. Assuming exponential DFS times, this corresponds to m_S =median time to failure for standard therapy of 32.6 months¹³. We will then assume that m_S follows an inverse gamma (31.52, 994.99) distribution, which corresponds to a median time to failure of 32.6 months and a corresponding standard deviation of 6 months. For the experimental group, m_E = median time to failure with the experimental therapy will be assumed to have the same mean but large variance: $a_E=3$ and $b_E=65.2$. Monitoring possibly right-censored T continuously, the trial will be terminated early if $\Pr(m_S < m_E | \text{data}) < 0.1878$. The expected accrual rate is 1 patient per month, and a maximum of 37 patients will be treated. The monitoring rules were conducted by using the MDACC Department of Biostatistics software: TTEDesigner program v1.2.2. The operating characteristics of this safety monitoring rule are summarized in Table 5, based on 2000 replications per scenario.

Table 5. Operating characteristics of the safety and efficacy monitoring rule

True Pr(F2YR)	True Median Time to Failure (Months)	Pr(Stop Early)	Mean Sample Size
0.20	74.5	0.100	34.0
0.30	46.6	0.238	30.5
0.40	32.6	0.470	25.4
0.50	24.0	0.775	19.0
0.60	18.2	0.947	13.7

Safety Run-in

At any time within first 6 patients are treated, if ≥ 2 patients experience serious adverse events (SAE) within first 3 cycles of treatment, we will stop the trial and claim that the regimen is too toxic. An SAE is defined as an adverse event that is serious, unexpected, and related to the study drug. This study will be monitored by the IND Office. During the safety run-in and throughout the study, patients who have completed 3 cycles of treatment will be considered as evaluable for safety and response.

Analysis of Primary and Secondary Endpoints

The primary endpoint of DFS will be summarized at 2 years with a corresponding 95% confidence interval. DFS will be compared with the historical control rate of 60% at year two by using a one-sided exponential MLE test. Cox proportional hazards regression analysis will be used to model the association between DFS and disease and demographic covariates of interest, including immune-related biomarkers in the peripheral blood and tumor tissue. Overall survival (OS) from the start of the study will be analyzed similarly to DFS. Adverse events will be summarized by grade and category.

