7.0 SAFETY MONITORING AND REPORTING

7.1 Assessing and Reporting Adverse Event

An adverse event is defined as any untoward medical occurrence in a patient or clinical investigation subject administered a pharmaceutical product and which does not necessarily have to have a causal relationship with this treatment. An adverse event can therefore be any unfavorable and unintended sign (including an abnormal laboratory finding, for example), symptom, or disease temporally associated with the use of a medicinal product or protocol-specified procedure, whether or not considered related to the medicinal product or protocol-specified procedure. Any worsening (i.e., any clinically significant adverse change in frequency and/or intensity) of a preexisting condition that is temporally associated with the use of the pembrolizumab, is also an adverse event.

Adverse events may occur during the course of the use of pembrolizumab in clinical trials, or as prescribed in clinical practice, from overdose (whether accidental or intentional), from abuse and from withdrawal.

Progression of the cancer under study is not considered an adverse event.

All adverse events that occur after the consent form is signed but before treatment allocation/randomization must be reported by the investigator if they cause the subject to be excluded from the trial, or are the result of a protocol-specified intervention, including but not limited to washout or discontinuation of usual therapy, diet, placebo treatment or a procedure.

From the time of treatment allocation through 30 days following cessation of treatment, all adverse events must be reported by the investigator. Such events will be recorded at each examination on the Adverse Event case report forms/worksheets. The reporting timeframe for adverse events meeting any serious criteria is described in section [7.6](#). The investigator will make every attempt to follow all subjects with non-serious adverse events for outcome.

Adverse events will not be collected for subjects during the pre-screening period as long as that subject has not undergone any protocol-specified procedure or intervention.

Adverse events will be assessed according to the CTCAE version 4.0. All study patients who have received any dose of pembrolizumab will be evaluable for safety. Unexpected adverse events including laboratory adverse events deemed clinically significant by the investigator will be graded and recorded.

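### The monitored outcome T is written as time to relapse although the endpoint is DFS, so a literal reading leaves deaths without relapse uncounted; the safety-evaluable set is also defined in two conflicting ways

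*Combined protocol and SAP*

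**What the plan says.** **Endpoint and rule (Section 8.0).** The Overview states: "The primary endpoint is Disease-free survival (DFS) as evidenced by the patient remaining alive with continued disease control". It then says: "We will use a Bayesian time-to-event monitoring design to monitor DFS to ensure patient safety". Under Disease-Free Survival Monitoring Rule the monitored variable is given as: "The primary outcome is T = the time to disease relapse". Failure is T below 2 years. The comparator is a historical two-year DFS rate of 60%, and the complementary 40% is glossed as relapse. DFS times are assumed exponential. Section 3.1.3 calls the same 60% a PFS rate. The text then says: "The operating characteristics of this safety monitoring rule are summarized in Table 5".

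**Who is evaluable for safety.** The Safety Run-in stops the trial "if ≥ 2 patients experience serious adverse events (SAE) within first 3 cycles of treatment, we will stop the trial", among the first 6 patients. It also says, for the run-in and for the rest of the study, that "patients who have completed 3 cycles of treatment will be considered as evaluable for safety and response". Section 7.1 says instead: "All study patients who have received any dose of pembrolizumab will be evaluable for safety".

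**Other text on deaths.** Section 4.6.1.1 treats deaths in the first 2 weeks owing to concurrent disease as failures in the intent-to-treat analysis. It does not define T and does not cover later deaths or toxic deaths.

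**The concern.** A stopping rule needs one event definition. The endpoint includes death and the comparator is a DFS rate, but T names only relapse. An analyst who codes T as written would enter a patient who dies without relapse as a censored time. A fatal toxicity would then not count as a failure in the rule that the plan presents as protecting patients.

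The label makes this harder to see. Table 5 is described as belonging to a safety monitoring rule, but T is the rule's only input. No adverse event, grade or serious event enters it. Safety is item 2 under the primary objective in Section 2.0, so a reader could credit Table 5 with protection that it does not describe.

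The two definitions of the safety set matter for the same objective. Under the Safety Run-in wording, a patient who stops for toxicity in cycle 1 or 2 has not completed 3 cycles and drops out of the safety set. These are the patients that a safety summary most needs.

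**Working it through.** **Inputs, all from Section 8.0.** Standard: m_S ~ inverse gamma (31.52, 994.99). Experimental: m_E ~ inverse gamma (3, 65.2). Stop if Pr(m_S < m_E | data) < 0.1878. Accrual 1 per month, maximum 37 patients.

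**Update.** For exponential times with median m_E, k failures and total follow-up F in patient-months:

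m_E | data ~ inverse gamma (3 + k, 65.2 + ln 2 × F).

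**Step 1: reproduce Table 5.** Simulation from failure times alone, Poisson accrual, rule checked at each new entry, 40,000 trials per row:

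| True Pr(F2YR) | Pr(stop), Table 5 | Pr(stop), recomputed | Mean N, Table 5 | Mean N, recomputed |
|---|---|---|---|---|
| 0.20 | 0.100 | 0.096 | 34.0 | 34.1 |
| 0.30 | 0.238 | 0.229 | 30.5 | 30.7 |
| 0.40 | 0.470 | 0.471 | 25.4 | 25.5 |
| 0.50 | 0.775 | 0.769 | 19.0 | 19.1 |
| 0.60 | 0.947 | 0.951 | 13.7 | 13.5 |

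The table is recovered with no toxicity component, so it describes DFS or relapse monitoring only.

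**Step 2: one data set, two readings.** Take F = 60 patient-months, 3 deaths without relapse and no relapses. The scale is 65.2 + 0.6931 × 60 = 106.79 under both readings.

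- Deaths censored: k = 0, m_E ~ inverse gamma (3, 106.79), Pr(m_S < m_E) = 0.643. The trial continues.
- Deaths counted: k = 3, m_E ~ inverse gamma (6, 106.79), Pr(m_S < m_E) = 0.137, below 0.1878. The trial stops.

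As a check, with 3 failures the rule stops whenever F is below 77.0 patient-months, and 60 is below that.

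**Step 3: operating characteristics under each reading.** Relapse median 74.5 months (20% relapse at two years). Non-relapse deaths occur in a fraction d of patients, uniformly over 24 months. The documents give no such death rate, so d is an assumed range. True two-year DFS failure is 1 − 0.80 × (1 − d).

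| d | True two-year DFS failure | Pr(stop), deaths censored | Pr(stop), deaths counted |
|---|---|---|---|
| 0 | 0.20 | 0.096 | 0.096 |
| 5% | 0.24 | 0.096 | 0.137 |
| 10% | 0.28 | 0.097 | 0.191 |
| 20% | 0.36 | 0.097 | 0.338 |

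Read literally, the rule behaves as if failure were 0.20 throughout, whatever the death rate.

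**Step 4: the safety set.** No arithmetic applies. Section 7.1 admits a patient to the safety set at the first dose. The Safety Run-in paragraph admits the same patient only after cycle 3 and extends this beyond the run-in. Both cannot hold for a patient who stops in cycle 1 or 2.

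**The case against.** The best defence is that the intent is clear enough. The rule's heading names DFS, the Overview says DFS is monitored, the endpoint and the sample-size statement both require the patient to be alive, and the model and comparator are for DFS. Nowhere does the plan say that a death is censored. This stands: Steps 2 and 3 measure the cost of an ambiguity, with assumed death rates, and do not show that the sponsor plans to ignore deaths. It does not remove the contradiction, because T and its failure rate are both described as relapse and no other section settles the matter.

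Table 5's columns are also headed by failure probability and time to failure, so a careful reader can see that toxicity is absent. That limits the harm of the label. Likewise, the run-in boundary counts patients who experience an event and does not say evaluable patients, so it is not shown that the run-in count itself loses early dropouts.

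Three stronger readings are tempting, and the documents do not support them:

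- *That uncounted toxic deaths push the rule towards continuing.* Pr(stop) is flat in Step 3. Pr(m_S < m_E) is 0.340 before any data and 0.643 at 60 failure-free patient-months, and that rise comes from the follow-up, whether or not anyone died. A censored death shortens follow-up. Twelve patients entering monthly with no deaths or relapses would contribute 66 to 78 patient-months, giving 0.667 to 0.711.
- *That known pembrolizumab toxicities can never trigger the run-in.* The run-in says: "An SAE is defined as an adverse event that is serious, unexpected, and related to the study drug". But the documents give no list of expected events for this purpose, and the remark in Section 4.2 about a known side effect profile justifies fewer physician visits.
- *That the trial lacks safety oversight after the run-in and needs a further numeric trigger.* No numeric trial-level toxicity boundary follows the run-in. However, Section 7.1 provides ongoing review, Section 7.4 sponsor review of aggregated safety data, Section 7.6.1 reporting of all serious events whether expected or not, Section 8.0 IND Office monitoring, and Table 3 patient-level discontinuation. Choosing judgement over a threshold is a debatable design choice and is not an error.

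**Conclusion.** The point holds as two wording contradictions and a misleading label, of minor to moderate severity.

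- T omits death while the endpoint and comparator include it. This can reverse a stopping decision (0.64 against 0.14, cutoff 0.1878). At 20% two-year relapse, Pr(stop) is about 0.10 under the literal reading and about 0.14, 0.19 and 0.34 with deaths counted, for non-relapse deaths in 5, 10 and 20% of patients. The sizes rest on the assumed death rates, deaths spread evenly over 24 months, exponential relapse times, and checks at each entry. If no patient dies without relapse, the two readings agree.
- The safety-evaluable set is any dose in Section 7.1 and 3 completed cycles in Section 8.0. The number of patients affected cannot be computed from the documents.
- The DFS rule and Table 5 carry no non-fatal toxicity input and should not be called safety monitoring.

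**What to change.** Amend the wording of Section 8.0 as follows.

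1. Define T as time from start of treatment to relapse or death from any cause. Keep the priors and the 0.1878 cutoff. The Table 5 numbers also stay, because its rows are indexed by the true two-year failure probability and apply to the combined event under the same exponential model. Relabel the rule and Table 5 as DFS (futility) monitoring, and drop the statement that DFS monitoring ensures patient safety.
2. In the Safety Run-in paragraph, let completion of 3 cycles define evaluability for response only. Use the any-dose set of Section 7.1 for all safety analyses, and state that it also applies to the run-in count.

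The cost is one wording amendment, with no extra patients, procedures or data. The statistical downside is a somewhat higher chance of early stopping than under the literal rule if non-relapse deaths occur, as shown in the last column of Step 3. That is how a DFS rule should behave.

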2.0 OBJECTIVE(S) & HYPOTHESIS (ES)

Primary Objective:

1. To determine the disease free survival (DFS) at 2 years of patients with maintenance therapy using pembrolizumab in combination with standard adjuvant hormonal therapy.

Hypothesis: Pembrolizumab maintains the disease-free status of patients with HR-positive primary IBC who have less than pathological complete response from neoadjuvant chemotherapy.

2. To determine the safety and toxicity profile of primary IBC patients who received combination of pembrolizumab and hormone receptor blockade.

Exploratory Objective

To investigate the association between immune related biomarkers in the peripheral blood and tumor tissue, such as PD-L1 expression, with safety and efficacy for IBC patients treated with pembrolizumab.

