4.2 Treatment Plan

The treatment to be used in this trial is outlined in Table 1 below.

Drug	Dose/Potency	Dose Frequency	Route of Administration	Regimen/ Treatment Period	Use
pembrolizumab	200 mg	Every 3 weeks	IV infusion	Up to 24 months or until meet drug discontinuation criteria (See 4.5)	Experimental

Drug	Dose/Potency	Dose Frequency	Route of Administration	Regimen/ Treatment Period	Use
The pembrolizumab dosing interval may be increased due to toxicity described in 4.2.2 .					

Based on our experience with very minimal side effects observed in the first 3 evaluable patients (see Table 2) as well as the design of another adjuvant Pembrolizumab study ongoing in triple negative breast cancer, physician follow-up will be reduced to every 2 cycles during the study due to the known side effect profile of Pembrolizumab.

Table 2: Interim safety analysis (3 evaluable patients, as of November 2017)

AE	Grade	Total # of patients
Fatigue	Grade 1	2
Nausea	Grade 1	1
Hot flashes	Grade 1	2
Headaches	Grade 1	1
Agitation	Grade 1	1
Skin itching	Grade 1	2
Vomiting	Grade 1	1
Dizziness	Grade 1	1
Eye disorders - eyelash thinning	Grade 1	1
Arthalgia	Grade 1	1
Rash	Grade 1	1

Based on emerging safety and efficacy data, as described in section 3.1.4, study treatment may be given concurrently with radiation based on physician and/or patient preference, but is not required. For patients consented prior to radiation who meet other eligibility criteria to allow concurrent radiation, pembrolizumab treatment will begin 7 days (± 3 days) after initiating radiation. During radiation, adverse events will be collected weekly, and patients will continue twice-weekly/weekly follow up visits with radiation oncologists as per standard procedure at MD Anderson for IBC patients receiving radiation. Special attention will be placed to minimize off-target dose to the lung, owing to the risk for pneumonitis in patients receiving immune checkpoint therapy.

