7.5 Evaluating Adverse Events

An investigator who is a qualified physician will evaluate all adverse events according to the NCI Common Terminology for Adverse Events (CTCAE), version 4.0. Any adverse event which changes CTCAE grade over the course of a given episode will have each change of grade recorded on the adverse event case report forms/worksheets.

All adverse events regardless of CTCAE grade must also be evaluated for seriousness.

An investigator who is a qualified physician, will evaluate all adverse events as to:

V4.0 CTCAE Grading	Grade 1	Mild; asymptomatic or mild symptoms; clinical or diagnostic observations only; intervention not indicated.
	Grade 2	Moderate; minimal, local or noninvasive intervention indicated; limiting age-appropriate instrumental ADL.
	Grade 3	Severe or medically significant but not immediately life-threatening; hospitalization or prolongation of hospitalization indicated; disabling; limiting self-care ADL.
	Grade 4	Life threatening consequences; urgent intervention indicated.
	Grade 5	Death related to AE

Seriousness	A serious adverse event is any adverse event occurring at any dose or during any use of Merck product that:
	† Results in death ; or
	† Is life threatening ; or places the subject, in the view of the investigator, at immediate risk of death from the event as it occurred (Note: This does not include an adverse event that, had it occurred in a more severe form, might have caused death.); or
	† Results in a persistent or significant disability/incapacity (substantial disruption of one's ability to conduct normal life functions); or
	† Results in or prolongs an existing inpatient hospitalization (hospitalization is defined as an inpatient admission, regardless of length of stay, even if the hospitalization is a precautionary measure for continued observation. (Note: Hospitalization for an elective procedure to treat a pre-existing condition that has not worsened is not a serious adverse event. A pre-existing condition is a clinical condition that is diagnosed prior to the use of a Merck product and is documented in the patient's medical history.); or
	† Is a congenital anomaly/birth defect (in offspring of subject taking the product regardless of time to diagnosis); or
	Is a new cancer (that is not a condition of the study) (although not serious per ICH definition, is reportable to the Sponsor and Merck); or

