7.6 SERIOUS ADVERSE EVENT REPORTING

7.6.1 Reporting to IND Office

An adverse event or suspected adverse reaction is considered “serious” if, in the view of either the investigator or the sponsor, it results in any of the following outcomes:

- Death
- A life-threatening adverse drug experience – any adverse experience that places the patient, in the view of the initial reporter, at immediate risk of death from the adverse experience as it occurred. It does not include an adverse experience that, had it occurred in a more severe form, might have caused death.
- Inpatient hospitalization or prolongation of existing hospitalization
- A persistent or significant incapacity or substantial disruption of the ability to conduct normal life functions.
- A congenital anomaly/birth defect.

Important medical events that may not result in death, be life-threatening, or require hospitalization may be considered a serious adverse drug experience when, based upon appropriate medical judgment, they may jeopardize the patient or subject and may require medical or surgical intervention to prevent one of the outcomes listed in this definition. Examples of such medical events include allergic bronchospasm requiring intensive treatment in an emergency room or at home, blood dyscrasias or convulsions that do not result in inpatient hospitalization, or the development of drug dependency or drug abuse (21 CFR 312.32).

- Important medical events as defined above, may also be considered serious adverse events. Any important medical event can and should be reported as an SAE if deemed appropriate by the Principal Investigator or the IND Sponsor, IND Office.
- All events occurring during the conduct of a protocol and meeting the definition of a SAE must be reported to the IRB in accordance with the timeframes and procedures outlined in “University of Texas M. D. Anderson Cancer Center Institutional Review Board Policy for Investigators on Reporting Unanticipated Adverse Events for Drugs and Devices”. Unless stated otherwise in the protocol, all SAEs, expected or unexpected, must be reported to the IND Office, regardless of attribution (within 5 working days of knowledge of the event).

- All life-threatening or fatal events, that are unexpected, and related to the study drug, must have a written report submitted within 24 hours (next working day) of knowledge of the event to the Safety Project Manager in the IND Office.

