- Unless otherwise noted, the electronic SAE application (eSAE) will be utilized for safety reporting to the IND Office and MDACC IRB.
- Serious adverse events will be captured from the time of the first protocol-specific intervention, until 30 days after the last dose of drug, unless the participant withdraws consent. Serious adverse events must be followed until clinical recovery is complete and laboratory tests have returned to baseline, progression of the event has stabilized, or there has been acceptable resolution of the event.
- Additionally, any serious adverse events that occur after the 30 day time period that are related to the study treatment must be reported to the IND Office. This may include the development of a secondary malignancy.
- Notable events must be recorded in the eSAE program in order to be submitted to sponsor. Reporting of notable events is the responsibility of the investigator.

7.6.2 Reporting to FDA:

- Serious adverse events will be forwarded to FDA by the IND Sponsor (Safety Project Manager IND Office) according to 21 CFR 312.32.

It is the responsibility of the PI and the research team to ensure serious adverse events are reported according to the Code of Federal Regulations, Good Clinical Practices, the protocol guidelines, the sponsor's guidelines, and Institutional Review Board policy.

7.6.3 Investigator Communication with Supporting Companies:

The MDACC Internal SAE Report Form will be used for reporting to Merck Global Safety ([contact]).

Reporting Timeline:

- Deaths that is unanticipated and definitely, probably or possibly related to study intervention that occur during and within 30 days after the last day of active study intervention will be reported to Merck within 24 working hours.
- All other SAEs that are serious, unanticipated, and definitely, probably or possibly related to study drugs will be reported to Merck within 2 working days.

Non-serious Events of Clinical Interest will be forwarded to Merck Global Safety and will be handled in the same manner as SAEs.

Immediate Reporting of Adverse Events to Merck:

Serious Adverse Events

A serious adverse event is any adverse event occurring at any dose or during any use of Merck's product that:

- Results in death;
- Is life threatening;
- Results in persistent or significant disability/incapacity;
- Results in or prolongs an existing inpatient hospitalization;
- Is a congenital anomaly/birth defect;
- Is another important medical event

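### The run-in calls the regimen too toxic only on unexpected events, so serious drug-related events classed as expected cannot count toward the trial's only numeric toxicity threshold

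*Combined protocol and SAP*

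**What the plan says.** Section 8.0 (Safety Run-in) stops the trial, with the conclusion that the regimen is too toxic, once 2 or more of the first 6 treated patients have had an SAE in cycles 1 to 3. The same paragraph defines the counted event: "An SAE is defined as an adverse event that is serious, unexpected, and related to the study drug".

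The safety sections use the term differently. Section 7.5 begins its definition with "A serious adverse event is any adverse event occurring at any dose or during any use of Merck product that" and lists outcomes, with no condition on expectedness or relatedness. Section 7.6.1 also defines seriousness by outcome and adds that "all SAEs, expected or unexpected, must be reported to the IND Office, regardless of attribution".

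Conditions like the run-in's appear elsewhere only as reporting filters. Section 7.6.1 states: "All life-threatening or fatal events, that are unexpected, and related to the study drug, must have a written report submitted within 24 hours". Section 7.6.3 sets a reporting deadline for "SAEs that are serious, unanticipated, and definitely, probably or possibly related to study drugs".

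Section 2.0 lists this under the primary objective: "To determine the safety and toxicity profile of primary IBC patients who received combination of pembrolizumab and hormone receptor blockade". Section 8.0 says that adverse events will be summarised by grade and category, without an expectedness filter.

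**The concern.** One term has two meanings, and the narrower one drives a conclusion about toxicity. Whether an event is unexpected is a question about prior knowledge of the drug. Whether a regimen is too toxic is a question about how often patients are seriously harmed by it. Section 8.0 answers the second question with a count filtered by the first and gives no reason for doing so.

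The filter could matter here. Section 4.2 relies on the drug's known side-effect profile, and Sections 4.2.2 (Table 3) and 4.4 anticipate colitis, pneumonitis, hepatic events, nephritis, hypophysitis and others. Serious forms of these could plausibly be classed as expected, although no document says so. If they are, the run-in could be completed without stopping despite an excess of serious drug-related events. Section 8.0 also names no reference document for the expectedness call.

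**Working it through.** **Does any other rule supply the missing threshold?**
- Bayesian monitoring (Section 8.0): the boundary is on median time to failure, and T is defined as time to relapse. Toxicity is not an input. The Overview, however, describes the endpoint as being alive with disease control, so on that reading a toxic death would be a failure. Non-fatal toxicity is not counted on either reading.
- Table 3 (Section 4.2.2) and Section 4.5 act on individual patients.
- Sponsor review of aggregate data (Section 7.4), SAE reports to the IND Office (Section 7.6.1) and IND Office monitoring (Section 8.0) carry no number.

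The run-in is therefore the only numeric trial-level toxicity threshold.

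**How much could the filter change?** The plan gives no figure to reproduce. Table 5 covers only the disease-free survival rule, and the run-in has no stated operating characteristics.

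Inputs: n = 6 and a threshold of 2, from Section 8.0. Two quantities are assumed, because the documents give neither:
- q, the per-patient probability of a serious drug-related event in cycles 1 to 3;
- s, the share of affected patients with at least one such event classed as unexpected.

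With patients independent and p = q × s, stopping as soon as a second patient counts is the same event as reaching 2 or more of 6:

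P(stop) = 1 − (1 − p)^6 − 6p(1 − p)^5

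Worked at q = 20%:
- s = 100%, p = 0.20: 1 − 0.2621 − 0.3932 = 0.345
- s = 50%, p = 0.10: 1 − 0.5314 − 0.3543 = 0.114
- s = 0%, p = 0: 0

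| Assumed q | s = 100% | s = 50% | s = 20% | s = 0% |
|---|---|---|---|---|
| 10% | 11.4% | 3.3% | 0.6% | 0% |
| 20% | 34.5% | 11.4% | 2.2% | 0% |
| 30% | 58.0% | 22.4% | 4.6% | 0% |
| 40% | 76.7% | 34.5% | 7.7% | 0% |

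The last column needs no assumption about q. If no event is classed as unexpected, the rule cannot trigger, even if all 6 patients have a serious drug-related event.

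**Effect of the data already seen.** Section 4.2 reports Grade 1 events only and cuts physician visits: "Based on our experience with very minimal side effects observed in the first 3 evaluable patients". Suppose those 3 are among the first 6 treated and no other treated patient has had a counted event. Then 2 of the remaining 3 must count, with P = 3p²(1 − p) + p³. At q = 20% this is 0.096 + 0.008 = 10.4% for s = 100%, and 0.027 + 0.001 = 2.8% for s = 50%. Zero events in 3 patients is weak reassurance: the one-sided 95% upper bound is 1 − 0.05^(1/3) = 63%.

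**The case against.** The strongest reply is that this is a deliberate choice. Pembrolizumab enters with a large safety record, its immune toxicities already have per-patient rules, and a six-patient run-in aimed at new toxicity of the combination is coherent. The counted event is defined explicitly, so nobody applying the rule need be confused. That reading is possible, but the protocol never states it, and it does not fit the rule's own conclusion, which is that the regimen is too toxic and not that a new signal has appeared.

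Several limits on the point do stand.
- A reader might infer that expected serious events would go unseen. The documents do not support that. Section 7.6.1 sends all SAEs to the IND Office, Section 7.4 provides aggregate review, and Table 2 is an interim safety table with no expectedness filter.
- A reader might infer that the primary safety objective cannot be met. It is also served by the unfiltered adverse event summary in Section 8.0.
- A reader might infer that the protocol treats passing the run-in as proof of acceptable toxicity. Section 8.0 draws a conclusion only when the threshold is crossed.
- The missing source for expectedness is a small gap. The heading of Section 3.1.2 names the Investigator's Brochure and Sections 7.6.1 and 7.6.2 cite 21 CFR 312.32, but neither is tied to the run-in.
- Counting more events while keeping 2 of 6 raises the chance of stopping. That is a real cost.

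**Conclusion.** The point holds as a defect in the stopping count and should be fixed. It follows from the wording alone that serious drug-related events classed as expected cannot contribute to the only numeric trial-level toxicity threshold, and that the definition in Section 8.0 disagrees with those in Sections 7.5 and 7.6.1.

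The size is not known. Every non-zero probability above rests on an assumed event rate and an assumed unexpected share. At a 20% rate, the filter lowers the chance of stopping from 34% to 11% if half of affected patients have an unexpected event, and to 0% if none do. That Table 3 toxicities would be classed as expected is an inference. It would go too far to say that the filter has hidden a toxic regimen, or that the Bayesian rule can never respond to a toxic death.

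The run-in may already be over. Three patients were evaluable by November 2017, planned accrual is 1 per month, and the reference list includes a June 2018 paper, but completion is not documented.

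**What to change.** 1. Reconcile Sections 7.5, 7.6.1 and 8.0 so that the run-in's toxicity conclusion does not depend on expectedness. Give the counted event its own name instead of SAE, and say that requiring relatedness is deliberate, since the other two definitions do not require it.
2. State in Section 8.0 the stopping probabilities of the 2-of-6 rule for the event chosen. For related SAEs regardless of expectedness they are 11%, 34%, 58% and 77% at rates of 10%, 20%, 30% and 40%. The protocol gives no tolerable rate, so the team must confirm that the threshold is acceptable for that event.
3. If the unexpected condition is kept, narrow the stated conclusion to a new-toxicity signal, give the reason, and name the document that decides expectedness.
4. Because some data had been seen by November 2017, date the change and tabulate the first 6 treated patients under both definitions. Use treated patients: Section 7.1 says "All study patients who have received any dose of pembrolizumab will be evaluable for safety", whereas Section 8.0 calls patients evaluable only after 3 cycles. If the run-in is complete, this tabulation is the remaining action.

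The cost is a short edit, a four-row table, and a six-patient tabulation from reports that Section 7.6.1 already requires. The downside is a higher chance of stopping in the run-in: at an assumed 20% rate, 34% against 11% if half of affected patients have an unexpected event, or 10% against 3% under the conditional assumptions above.
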